#### **13.6 Reporting to Hospital Risk Management**

Participating investigators will report to their local Risk Management office any subject safety reports or sentinel events that require reporting according to institutional policy.

#### **13.7 Monitoring of Adverse Events and Period of Observation**

All adverse events, both serious and non-serious, and deaths that are encountered from initiation of study intervention, throughout the study, and within 30 days of the last study intervention should be followed to their resolution, or until the participating investigator assesses them as stable, or the participating investigator determines the event to be irreversible, or the participant is lost to follow-up. The presence and resolution of AEs and SAEs (with dates) should be documented on the appropriate case report form and recorded in the participant's medical record to facilitate source data verification.

CONFIDENTIAL

This document is confidential. Do not disclose or use except as authorized.

For some SAEs, the study sponsor or designee may follow-up by telephone, fax, and/or monitoring visit to obtain additional case details deemed necessary to appropriately evaluate the SAE report (e.g., hospital discharge summary, consultant report, or autopsy report).

Participants should be instructed to report any serious post-study event(s) that might reasonably be related to participation in this study. Participating investigators should notify the MSSM Overall Principal Investigator and their respective IRB of any unanticipated death or adverse event occurring after a participant has discontinued or terminated study participation that may reasonably be related to the study.

## 14 DATA AND SAFETY MONITORING

### 14.1 Data Reporting

#### Method

The Study team and the CCTO will collect, manage, and monitor data for this study.

#### Data Submission

The schedule for completion and submission of case report forms (paper or electronic) to the QACT is as follows:

Form/eCRF	Estimated Submission Timeline
Eligibility Checklist	Complete prior to registration with MSSM
On Study Form	Within 14 days of registration
Baseline Assessment Form	Within 14 days of registration
Treatment Form	Within 10 days of the last day of the cycle
Adverse Event Report Form	Within 10 days of the last day of the cycle
Response Assessment Form	Within 10 days of the completion of the cycle required for response evaluation
Off Treatment/Off Study Form	Within 14 days of completing treatment or being taken off study for any reason
Follow up/Survival Form	Within 14 days of the protocol defined follow up visit date or call

### 14.2 Safety Meetings

Because this is a Phase II trial an internal Data Safety Monitoring Board will be required to review and monitor toxicity, accrual data from this trial and interim results on this trial. The committee will be composed of [name] (Chair), [name], [name], [name] and the statistician. The

CONFIDENTIAL

This document is confidential. Do not disclose or use except as authorized.

Review group will meet quarterly to review survival and recurrence data from the trial. An independent MSSM statistician shall be a member. The chairman of the DSMB will prepare minutes and report to the DSMC. The study report will remain blinded for efficacy results unless there is sufficient reason for the DSMB to consider halting the trial.

The DSMB will meet semi-annually and/or more often if required to review toxicity and accrual data. Information to be provided to the committee may include: up-to-date participant accrual; all unexpected adverse events that have been reported; summary of all surgical complications or deaths while being treated and during active follow-up; any response information; audit results, and a summary provided by the study team. Other information (e.g. scans, laboratory values) will be provided upon request.

**Adverse Events.** safety data, including all protocol-defined and serious unanticipated adverse events, will be collected throughout the entire course of the study. Expedited reporting to the IRB and study sponsor will be required for any unexpected serious adverse event.

#### Reporting of Serious Adverse Events

All investigators NHLBI must report both expected (protocol defined) and unexpected serious adverse events. All serious adverse events must be reported directly to the clinical center's IRB within 10 working days of knowledge of the event, or as dictated by the specific IRB policy, whichever is sooner. All deaths and unexpected serious adverse events must be reported to the IRB within 24 hours of knowledge of the event, or as dictated by the specific IRB policy, whichever is sooner. The investigators will notify the study sponsor of any deaths and unexpected serious adverse events via e-mail within 24 hours of receipt of the event. These events will also be reported to the DSMB chair within 72 hours of notification. All serious adverse events will be reported to the DSMB at least semi-annually, at the discretion of the DSMB. In addition, the investigators are expected to comply with their institutional policies and reporting requirements.

After recruitment of half of the study subjects (100) a full dataset analysis will be performed by the investigators and the statistical support group to ensure that outcomes are comparable to current standards. This will include statistical analysis of adverse events, recurrence rates after surgical therapy, outcomes of adjuvant therapy arms, and disease specific survival. Deviation from the proposed recurrence rates or overall disease specific survival will result in halting the trial. The primary endpoints are DFS and LRC at 3 and 5 years. Kaplan-Meier curves will be estimated for the standard therapy and the experimental therapy groups. Ninety-percent one-sided confidence intervals will be calculated for DFS at 3 and 5 years in the surgical and surgical/adjuvant therapy groups. The secondary endpoint of overall survival will be analyzed using Kaplan-Meier curves and a log-rank test for the difference between the two therapy groups. Five year OAS, DFS and LRC will be calculated using a log-rank test will be used to test for differences between the two treatment groups. Toxicity is another secondary endpoint. We will compute for each arm the toxicity rate and provide the corresponding 90% confidence intervals based on the exact binomial distribution.

#### Stopping Boundaries: Based on stopping if the probability that recurrence exceeds 50% is $\geq 0.80$

The following are greater-than-or-equal boundaries:

a pair (n, m) means to stop if the number of adverse events after treating m patients is greater than or equal to n.

n (# events)	m (# patients)	n (# events)	m (# patients)
7	10	35	62
8	12	36	64
9	14	37	66

CONFIDENTIAL

This document is confidential. Do not disclose or use except as authorized.

10	16	39	69
11	18	40	71
13	21	41	73
14	23	42	75
15	25	43	77
16	27	44	79
17	29	46	82
19	32	47	84
20	34	48	86
21	36	49	88
22	38	50	90
23	40	51	92
25	43	52	94
26	45	54	97
27	47	55	99
28	49	55	100
29	51		
30	53		
32	56		
33	58		
34	60		
35	62		

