### 16.2 Sample Size/Accrual Rate

Sample size justification:

The proposed sample size of 100 for Group 1 has been determined to ensure that an upper bound for recurrence may be estimated with adequate precision, defined as within 8-12% of the true recurrence rate. The upper bound is estimated by the posterior probability of recurrence given the observed data, assuming a non-informative beta(1,1) prior distribution. The table below provides the upper 95% bound (from the Bayesian credible interval) assuming the true rate of recurrence is .1,.2,.3,.4, or .5 and 100 patients are studied.

True recurrence	Upper 95% bound
.1	.184
.2	.301
.3	.413
.4	.516

CONFIDENTIAL

This document is confidential. Do not disclose or use except as authorized.

[figure not shown]

.5

.614

The various specific aims outlined in Aim 1 share a common objective: determining rates of important measures of treatment response (progression-free survival, overall survival, local regional control and ultimate disease control) for patients treated with surgery alone and compare them to those expected in patients with similar diagnostic criteria. We will assess this overall objective by using a Bayesian approach to estimate the posterior probability distributions for each respective sub-aim based on observed outcomes. This approach permits estimating probabilities with which a specified rate of interest exceeds a threshold value (e.g.; 50% local regional control, 85% overall survival, etc.)

Our approach begins with the premise that surgery alone offers no improvement in expected outcomes. This is an exact correspondence to a "null hypothesis". We incorporate this assumption through a prior distribution for each suspected rate; for example, for Group I patients we would assume that the rate of local regional control (LRC) at three years is 50%. After the studies are conducted, each respective rate is combined with the "null" prior distribution through Bayes' Theorem to yield the posterior distribution for the rate. The table below depicts simulated results for the posterior LRC ( $\theta$ ) using 100 patients based on two differing assumptions: that LRC at three years is 50% ( $p=0.5$  shown on the left) and 85% ( $p=0.85$  shown on the right).

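### Six of the 43 printed stopping pairs are one event higher than the stated rule requires under the plan's only fully specified prior, so the rule and its table disagree at late looks

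*Combined protocol and SAP*

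**What the plan says.** The Stopping Boundaries part of Section 14.2 defines the rule in its heading: "Based on stopping if the probability that recurrence exceeds 50% is" 0.80 or more. It then explains how to read the table: "a pair (n, m) means to stop if the number of adverse events after treating m patients is greater than or equal to n". The table has 43 distinct pairs, from 7 events in 10 patients to 55 in 100. (The pair 35/62 is printed twice.)

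The section names no prior. Section 16.2 gives one with parameters, in the sample-size argument for the recurrence bound: "assuming a non-informative beta(1,1) prior distribution". It also describes a prior centred on a null value, "We incorporate this assumption through a prior distribution for each suspected rate", with 50% local-regional control in Group I as the example, but it does not say how strong that prior is.

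The table ends at 100 patients, which matches Group I: "The proposed sample size of 100 for Group 1 has been determined". I read the table's events as recurrences, as the heading implies, although the reading instruction calls them adverse events.

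**The concern.** The cut-off, the 50% reference and the inclusive form of the boundary are all stated. Once a prior is chosen, each boundary is a single integer, so rounding cannot explain a mismatch. If a printed integer is too high, there are counts at which the rule says stop and the table says continue. This is the plan's only tabulated stopping boundary, and Section 15.6 makes the Protocol Chair responsible for initiating stopping rules at all sites. A monitoring board should not be able to get two answers from it.

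**Working it through.** **Inputs.** Cut-off 0.80, reference rate 50% and the 43 pairs come from Section 14.2. The Beta(1,1) prior comes from Section 16.2; applying it to the stopping rule is an assumption.

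**Formula.** With n recurrences in m patients the posterior is Beta(1+n, 1+m−n). The boundary at m is the smallest n with P(θ > 0.5 | Beta(1+n, 1+m−n)) ≥ 0.80. For this prior, the probability equals P(X ≤ n) for X binomial with m+1 trials and probability 0.5.

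**Rows that reproduce.** A printed n is right if its probability is at least 0.80 and that at n−1 is below 0.80. Examples:

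| Printed pair | at n | at n−1 |
|---|---|---|
| 7/10 | 0.887 | 0.726 |
| 17/29 | 0.8192 | 0.708 |
| 39/69 | 0.859 | 0.7985 |
| 44/79 | 0.843 | 0.783 |
| 55/100 | 0.840 | 0.787 |

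In all, 37 of 43 rows pass, including every row up to 79 patients.

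**Rows that do not.** In six rows, one event fewer already meets the rule:

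| Printed pair | at n | at n−1 | 0.80 boundary |
|---|---|---|---|
| 46/82 | 0.864 | 0.810 | 45/82 |
| 47/84 | 0.861 | 0.807 | 46/84 |
| 48/86 | 0.858 | 0.804 | 47/86 |
| 49/88 | 0.856 | 0.802 | 48/88 |
| 54/97 | 0.867 | 0.818 | 53/97 |
| 55/99 | 0.864 | 0.816 | 54/99 |

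For the first row, P(X ≤ 45) with X ~ Bin(83, 0.5) is 0.8100. No printed row is too low.

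**Which cut-off would fit.** Over all 43 rows, the smallest probability at a printed n is 0.8192 (17/29) and the largest at n−1 is 0.8183 (53/97). Under Beta(1,1) with 50% fixed, only a cut-off above 0.8183 and up to 0.8192 reproduces the table. A cut-off of 0.82 would not, because 17/29 falls short of it.

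**Other priors at 0.80, with 50% fixed.**

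| Prior | rows matching | too high | too low |
|---|---|---|---|
| Beta(0.5,0.5) | 35 | 8 | 0 |
| Beta(1,1) | 37 | 6 | 0 |
| Beta(2,2) | 38 | 5 | 0 |
| Beta(10,10) | 26 | 0 | 17 |

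A grid of asymmetric priors reached at most 41 of 43, for example Beta(0.4,0.8).

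**Size.** These are exact probabilities of ever stopping at the 43 printed looks, treating each patient's outcome as known at once:

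| True recurrence | Printed table | 0.80 rule, Beta(1,1) | Difference (points) |
|---|---|---|---|
| 50% | 52.9% | 54.1% | 1.2 |
| 55% | 79.6% | 80.9% | 1.3 |
| 60% | 95.3% | 95.9% | 0.6 |

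**The case against.** The strongest reply is that the table may be right and the description incomplete. Section 14.2 gives no prior, and Beta(1,1) is borrowed from the sample-size argument. If the 50% reference is itself uncertain, with a distribution between about Beta(150,150) and Beta(250,250), a 0.80 cut-off reproduces all 43 rows. This stands as a possibility. No section mentions such a distribution, however, and the heading gives a plain 50%. If that was the method, the stated rule is what needs correcting, so the mismatch on the page remains. The direction of the mismatch also depends on the prior: under Beta(10,10) the six rows are no longer too high, and 17 rows are too low.

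The effect is also small: one event, at six late looks. Section 14.2 provides other oversight through quarterly review of recurrence data and a full analysis after 100 subjects. That is fair and limits the severity.

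Four stronger readings are tempting but not supported:

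- **That the trial really uses a cut-off of 0.82.** The narrow window found above holds only for Beta(1,1) with 50% fixed, and it excludes 0.82.
- **That unlisted patient numbers are errors.** The table does not claim to list every m. Counts such as 24/42 (0.8198), 31/55 (0.825) and 38/68 (0.832) are unlisted although they meet even the cut-off that fits the table, so their absence says nothing about the threshold.
- **That the table is too strict at 42 of the 91 values of m from 10 to 100.** This assumes that an unlisted m takes the next listed row. If the previous row is carried forward instead, 6 values are stricter than the rule and 23 looser. The plan specifies neither.
- **That the chance of stopping is about 4.5 points too low.** Applying the rule at every m gives 57.4% at a true rate of 50%, against 52.9% for the table. Most of that gap comes from adding looks.

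**Conclusion.** As written, the rule and table disagree. Under Beta(1,1) with 50% fixed, 6 of 43 pairs are one event too high, all at 82 patients or more, and the other 37 are exact. No fixed-50% prior tried at 0.80 reproduces the whole table. The cost is about one percentage point of stopping probability at true recurrence of 50% to 55%, given immediate outcomes and looks at the printed numbers only.

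The count of six and its direction rest on the borrowed prior. What does not rest on it is that the section omits what is needed to regenerate its own table. A reader might infer that the boundary leaves patients materially less protected; the figures do not support that. Severity is minor to moderate: worth correcting because it is a safety boundary, but not an obstacle to the trial.

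**What to change.** State beside the table the prior used, whether 50% is a fixed value or a distribution, and that the events counted are recurrences. Then make rule and table agree in one of two ways:

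- **Keep the 0.80 rule and regenerate the table.** With Beta(1,1) and 50% fixed, the six pairs become 45/82, 46/84, 47/86, 48/88, 53/97 and 54/99. Printing every m from 10 to 100 is preferable, because quarterly reviews will often fall on an unlisted m and the plan does not say what to do there.
- **Keep the table and correct the stated rule** to the one that generated it. If that was Beta(1,1) with 50% fixed, the cut-off must lie above 0.8183 and no higher than 0.8192. If the reference was uncertain, give its distribution. Either way, say how an unlisted m is handled.

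The cost is one table or one or two sentences, with no change to sample size, visits or patient procedures.

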These pre-clinical studies conducted by Hockstein and the University of Pennsylvania group led the way for several preliminary clinical cohort studies. O'Malley et al. described the first series of TORS tongue base resections for squamous cell carcinoma. In this report, he outlined the surgical technique and advantages and disadvantages of the multiple retraction systems used during transoral tongue base surgery. All three patients were eating a full diet within 6 weeks. Weinstein et al. subsequently reported the use of the robot for supraglottic surgery with a series of 3 patients undergoing robotic supraglottic laryngectomy. Solares et al. followed shortly thereafter with a report of a supraglottic laryngectomy performed using a CO2 laser. The University of Pennsylvania group also reported the first series of TORS cases for radical tonsillectomy on 27 patients. The technical aspects of the surgery were described to allow for negative margin resection of tonsil malignancies while protecting the internal carotid artery in the parapharyngeal space. In this early series, all patients had gastrostomy tubes inserted prophylactically and one patient had planned tracheostomy. An additional patient had unexpected tracheostomy following exacerbation of pre-existing obstructive sleep apnea. The surgical complication rate was 19% including one mucosal hemorrhage requiring a return to the operating room, one tracheostomy, two patients developed trismus, and one patient developed hypernasality requiring an outpatient procedure for correction. [name] et al. and the Mount Sinai group published their institutional experience with their first 20 transoral robotic surgery cases. Two cases were aborted due to inadequate access and the remaining 18 cases consisted of 7 tonsil lesions, 4 tongue base lesions, 4 supraglottic lesions, 2 parapharyngeal lesions and 1 palate lesion. Patients did not require prophylactic gastrostomy tubes, and oral diet was achieved on 1.4 days after surgery on average. Patients were discharged on average 1.7 days after surgery. These investigations lead to FDA approval of transoral robotic surgery in 2009.

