## 13.0 ADVERSE EVENT REPORTING REQUIREMENTS

### 13.1 Definitions

#### 13.1.1 Adverse Event (AE)

An adverse event (AE) is any undesirable sign, symptom or medical condition or experience that develops or worsens in severity after starting the first dose of study treatment or any procedure specified in the protocol, even if the event is not considered to be related to the study.

Abnormal laboratory values or diagnostic test results constitute adverse events only if they induce clinical signs or symptoms or require treatment or further diagnostic tests.

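### The stopping table is built for recurrence, but the sentence that says how to apply it counts adverse events

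*Combined protocol and SAP*

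**What the plan says.** The heading of the Stopping Boundaries table in Section 14.2 gives its basis: "Based on stopping if the probability that recurrence exceeds 50% is" at least 0.80. The next lines explain how to read it: a pair (n, m) "means to stop if the number of adverse events after treating m patients is greater than or equal to n". The columns are labelled only as numbers of events and of patients, so the table does not settle which event is meant. The pairs run from 7 events in 10 patients to 55 in 100.

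Section 13.1.1 defines an adverse event as "any undesirable sign, symptom or medical condition or experience that develops or worsens in severity after starting the first dose of study treatment" or after any protocol procedure, and does not require a relation to the study. It sets no minimum grade.

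Elsewhere the protocol keeps the two events apart. Section 14.2 has survival and recurrence reviewed quarterly, and toxicity and accrual semi-annually. The planned analysis after 100 subjects lists adverse events and recurrence rates as separate items.

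The recurrence precision target in Section 16.2 concerns "The proposed sample size of 100 for Group 1" and is calculated "assuming a non-informative beta(1,1) prior distribution".

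**The concern.** A stopping rule has its stated property only if the event counted is the event for which the boundary was derived. Here the derivation concerns recurrence and the instruction concerns adverse events. In this protocol these are different events, with different frequencies and different review schedules.

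This is the trial's only numerical stopping boundary. The other halting provision, deviation from the proposed recurrence rates or disease-specific survival at the 100-subject analysis, carries no number. Group I receives no adjuvant treatment, so a boundary on recurrence is the protection that matters most there. Section 15.6 has the Protocol Chair initiate stopping rules at all sites and has triggers reported to the IRB, so people who did not write the rule will have to apply it as printed.

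**Working it through.** **Step 1: which event do the numbers belong to?**

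Inputs: threshold 0.50 and cutoff 0.80 (heading of the table, Section 14.2), and a beta(1,1) prior. Section 16.2 states that prior for the Group I recurrence bound. The stopping table states none, so using it here is an assumption.

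Formula: after n events in m patients the posterior is Beta(1+n, 1+m−n). The boundary at m is the smallest n with Pr(p > 0.50) ≥ 0.80.

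- m = 10: n = 6 gives 0.726 and n = 7 gives 0.887. The boundary is 7, as printed.
- m = 100: n = 54 gives 0.787 and n = 55 gives 0.840. The boundary is 55, as printed.

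Across the 43 distinct pairs (35 of 62 is printed twice), 37 match exactly. The other six are one event above the minimum: 46/82, 47/84, 48/86, 49/88, 54/97 and 55/99. For example, 45 of 82 already gives 0.810. Every printed pair meets the 0.80 cutoff; the lowest posterior is 0.819, at 17 of 29. The table is therefore the boundary that its heading describes.

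**Step 2: what the rule does when it counts recurrences**

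Exact recursion over the 43 printed looks, each outcome assumed known at once:

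| True recurrence rate | Probability of stopping by 100 patients |
|---|---|
| 10% | 0.00001 |
| 20% | 0.001 |
| 30% | 0.020 |
| 40% | 0.133 |
| 50% | 0.529 |
| 60% | 0.953 |

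**Step 3: what the printed sentence does when followed literally**

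The documents give no adverse event rate for this trial, so the rate is an assumption, shown over a range. Each patient with at least one event is counted once. The first look is P(Bin(10, p) ≥ 7). For p = 0.80 this is 0.2013 + 0.3020 + 0.2684 + 0.1074 = 0.879.

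| Assumed share of patients with an adverse event | Stop at first look (7 of 10) | Stop by 100 patients |
|---|---|---|
| 35% | 0.026 | 0.055 |
| 50% | 0.172 | 0.529 |
| 60% | 0.382 | 0.953 |
| 70% | 0.650 | 1.000 |
| 80% | 0.879 | 1.000 |
| 90% | 0.987 | 1.000 |
| 95% | 0.999 | 1.000 |

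The sentence counts events, not patients. If several events per patient are allowed (Poisson, simulated), the probability of stopping at 10 patients is about 0.87 with a mean of one event per patient, and about 0.9997 with a mean of two.

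None of the results in Step 3 depends on the recurrence rate.

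**The case against.** The strongest reply is that the intention is clear. The heading names recurrence, the threshold and the cutoff, the table ends at the Group I sample size, and the numbers reproduce as a recurrence boundary. Read by its heading, the rule has its stated property to within one event. This stands: it is most likely a wording slip, and the table itself is sound. It does not remove the defect, because the only operating sentence still names another defined event.

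Recurrence would also not go unwatched. It is reviewed quarterly, and the 100-subject analysis has its own halting provision. This too stands, although neither supplies a numerical boundary.

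Two stronger readings go further than the documents allow.

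- A reader might infer that the trial would stop almost at once or almost never. Stopping almost at once needs a high adverse event rate that the protocol does not state. Stopping almost never needs a narrower count, such as surgical complications only, which the sentence does not describe. The 19% complication rate in Section 2.2 comes from another institution's early series of 27 patients. At that rate the crossing probability is about 0.001, but a correct recurrence count at a true rate of 20% also crosses with probability about 0.001, so this does not separate the two events. Rates between 35% and 60% give 0.055 to 0.953, which is neither extreme.
- A reader might infer that the count should be limited to loco-regional recurrence, because the 50% hypothesis in Sections 16.1 and 16.2 concerns loco-regional control. The table heading, the 100-subject analysis and the precision table in Section 16.2 all say recurrence without that limit. Imposing it could bring in a new mismatch, so it is a question for the sponsor.

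**Conclusion.** The point holds as a contradiction within the stopping rule. The boundary is derived for recurrence, and its operating sentence counts adverse events. Taken literally, the rule is not tied to recurrence and does not deliver its stated property.

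The match to recurrence (37 of 43 pairs exact, six one event higher) rests on carrying the Section 16.2 prior over to the table. The size of the practical effect cannot be fixed from the documents. The 88% to 99.9% chance of stopping at 7 of 10 is an illustration under an assumed 80% to 95% of patients with any adverse event, and it treats outcomes as known at once.

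The documents also leave open who and what is counted. The maximum of 100 matches Group I in Section 16.2, but Section 14.2 also calls 100 half of the study subjects. Section 11.1.1 defines progression-free survival and loco-regional control, but not a recurrence event for counting.

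**What to change.** In the pair definition in Section 14.2, replace adverse events with *patients with recurrence, each patient counted once*. Add that adverse events are reviewed separately under Section 14.2 and do not enter this count.

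The sponsor should confirm, in the same place:

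- the group counted (Group I, if the maximum of 100 is meant to match Section 16.2);
- whether isolated distant recurrence counts, given that the heading says recurrence while the 50% hypothesis concerns loco-regional control;
- the follow-up at which a treated patient enters the denominator m.

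The cost is a short amendment to one paragraph. It needs no new data, and the boundary numbers can stay as printed.

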### **1.1 Primary Objectives**

- 1.1.1 To determine the rate of local regional control (LRC) at 5 years in patients with early and intermediate stage HPV related oropharynx cancer treated with surgery alone.
- 1.1.2 To determine the rate of progression free survival (PFS) at 5 years in patients with early and intermediate stage HPV related oropharynx cancer treated with surgery alone.
- 1.1.3 To determine overall survival (OS) at 5 years in patients with early and intermediate stage HPV related oropharynx cancer treated with surgery alone.
- 1.1.4 To determine the rate of local regional control (LRC) at 3 years in patients with HPV related oropharynx cancer treated with a de-intensified adjuvant protocol.
- 1.1.5 To determine the rate of progression free survival (PFS) at 3 years in patients with HPV related oropharynx cancer treated with a de-intensified adjuvant protocol.
- 1.1.6 To determine overall survival (OS) at 3 years in patients with HPV related oropharynx cancer treated with a de-intensified adjuvant protocol.
- 1.1.7 To determine the rate of PFS (Ultimate Disease Control – UDC) and of OAS after secondary therapy for patients treated with surgery only who have local regional relapse at 5 years
- 1.1.8 To determine the rate of PFS (UDC) and OAS after secondary therapy for patients who relapse with distant disease after surgery only
- 1.1.9 To quantify the quality of life of patients treated with this protocol at 3 years

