## 16.0 STATISTICAL CONSIDERATIONS

### 16.1 Study Design/Endpoints

This is a prospective clinical trial evaluating surgery alone for early stage HPV related oropharyngeal squamous cell carcinoma. The primary endpoints are the rate of local-regional control OAS, and PFS at 3 years in patients with HPV 16 and p16+ related head and neck cancer, treated with surgery alone. The secondary objectives include 5 year PFS, LRC, Overall Survival, Ultimate Disease Control, QOL, site of failure and rate of salvage, as well as establishing biomarkers predictive of treatment outcomes and collection of tumor tissue, germline DNA and a plasma bank for future studies. The main study hypotheses is that OAS and UDC at 5 years for surgery alone for early stage HPV related oropharyngeal squamous cell carcinoma is equivalent to current regimens involving standardized post-operative radiotherapy (>85%) and that LRC without radiotherapy will be > 50%. Additional Hypotheses relate to Group 2 and 3 - OAS and PFS at 5 years for reduced dose XRT and CRT intermediate stage HPV related oropharyngeal squamous cell carcinoma is equivalent to current regimens involving standardized post-operative radiotherapy (>85%) and that LRC will be > 85%.

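### The recurrence stopping boundary counts every treated patient as fully followed, so an uncrossed boundary during accrual does not show that P(recurrence > 50%) is below 0.80

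*Combined protocol and SAP*

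**What the plan says.** The heading of Stopping Boundaries (section 14.2) sets the criterion: "Based on stopping if the probability that recurrence exceeds 50"%, with the probability threshold at 0.80. Beneath it, a pair (n, m) means to "stop if the number of adverse events after treating m patients is greater than or equal to n". The pairs run from (7, 10) to (55, 100). The text speaks of adverse events where its heading speaks of recurrence, and it names no treatment group.

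The time point behind the 50% differs by section:

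- Section 16.2: "for Group I patients we would assume that the rate of local regional control (LRC) at three years is 50"%.
- Section 1.1.1, for surgery alone: "To determine the rate of local regional control (LRC) at 5 years in patients with early and intermediate stage HPV related" oropharynx cancer.
- Section 16.1: "that LRC without radiotherapy will be > 50"%, with no clear year.

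Two other provisions bear on recurrence. Section 14.2 says the "Review group will meet quarterly to review survival and recurrence data from the trial". After 100 patients are recruited, "Deviation from the proposed recurrence rates or overall disease specific survival will result in halting the trial". Neither gives a threshold. Section 11.1.1 makes patients evaluable for the primary outcomes on the basis of surgery alone, and section 6.1 sets five years of follow-up without linking it to the boundary.

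**The concern.** The posterior probability in the heading needs a numerator and denominator from the same, fully observed patients. The rule divides recurrences so far by everyone treated so far. While accrual continues, many of those patients have been at risk for only weeks or months, yet each enters as a non-recurrence.

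The error has a direction. If recurrence at any time is meant, a crossed boundary keeps its meaning, because later outcomes can only add events. An uncrossed boundary does not. If recurrence within three years is meant, the rule also errs the other way, because it counts recurrences after year 3.

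This is the only recurrence rule in the plan with event counts, and Group I receives no adjuvant therapy. A monitoring board that took an uncrossed boundary as reassurance could keep enrolling at a recurrence rate the rule was written to catch.

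**Working it through.** **1. Reproducing the printed pairs.** Section 16.2 states a Beta(1,1) prior for its precision bound; the boundary states none. Take the smallest n with P(p > 0.5 | Beta(1+n, 1+m−n)) ≥ 0.80.

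- m = 10: 7 events give 0.887, 6 give 0.726. Printed 7.
- m = 40: 23 give 0.826, 22 give 0.734. Printed 23.
- m = 100: 55 give 0.840, 54 give 0.787. Printed 55.

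This matches 37 of the 43 distinct pairs. At m = 82, 84, 86, 88, 97 and 99 the printed n is one higher than needed: one event fewer already gives 0.810, 0.807, 0.804, 0.802, 0.818 and 0.816. The formula has no term for patients still at risk.

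**2. Properties with all outcomes known.** An exact recursion over the listed m gives the probability of ever crossing at true recurrence 30 / 40 / 50 / 60 / 70%: 0.02 / 0.13 / 0.53 / 0.95 / 1.00.

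**3. Two illustrations (assumed data).**

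- Forty treated; ten have complete follow-up and eight of them recurred; the other thirty are recent, with no event yet. The rule compares 8 with 23 and continues: 8/40 gives a posterior of 0.0001. The ten complete patients alone give 0.967.
- Accrual of 20 per year, true three-year recurrence 70%, exponential timing. Hazard L = −ln(0.3)/3 = 0.401 per year. Patient 40 is treated at two years, so expected recurrences are 40 × [1 − (1 − e^(−2L))/(2L)] = 12.5, against a boundary of 23. Yet 0.70 × 40 = 28 of these patients will recur within three years.

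**4. Size during accrual.** The plan gives no overall accrual rate and no recurrence timing; its only figure is 5-10 patients per year from one added site (Appendix 4, Number of subjects). Both are therefore assumed. Simulation used Poisson accrual of 100 patients and the rule as written, so recurrences after year 3 count. Probability of stopping by patient 100, at true three-year recurrence 60% / 70%:

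| Accrual per year | Exponential, or all within 2 years | All within 1 year |
|---|---|---|
| 10 | 0.59-1.00 / 0.98-1.00 | 0.82-0.86 / 1.00 |
| 20 | 0.14-0.19 / 0.66-0.72 | 0.59-0.65 / 0.98-0.99 |
| 33 | 0-0.01 / 0.01-0.10 | 0.26-0.31 / 0.84-0.87 |
| Complete outcomes | 0.95 / 1.00 | 0.95 / 1.00 |

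Ranges also cover different look schedules. On a five-year horizon (true five-year rate, exponential timing) the figures are 0.49 / 0.92 at 10 per year and 0 / 0.01 at 20.

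**5. The opposite error.** If three years is meant, slow accrual over-stops. At 10 per year with exponential timing, the rule stops with probability 0.88-0.89 at true 50% (0.53 with complete outcomes) and 0.33-0.37 at true 40% (0.13).

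**6. Counting after accrual ends.** With all 100 followed, 55 events are reached with probability 0.87 to 1.00 at true 60%, depending on whether later recurrences count, and above 0.999 at 70%. By then enrolment is over.

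**The case against.** The strongest objection is that the size rests on inputs the plan does not give. At 10 per year with exponential timing there is no shortfall, and if every recurrence comes within a year the loss is modest. That stands, and the figures above are illustrative. They are not the worst case: counting only recurrences within 36 months lowers the 20-per-year exponential result to about 0.04 / 0.45, and even accrual lowers it further, to about 0.02 / 0.40. That an uncrossed boundary lacks its stated meaning does not depend on these inputs.

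Other safeguards exist: quarterly review of recurrence, an independent statistician on the board, and a halt for deviation. None has a threshold, and the interim analysis is triggered by recruitment, not by follow-up. Nor does the plan say that an uncrossed boundary is reassuring; that reading by the board is a supposition.

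Group I is also an inference. The table ends at 100, the Group 1 size in section 16.2 ("The proposed sample size of 100 for Group 1 has been determined to ensure" adequate precision), but 100 is also given as half of all subjects at the interim analysis, so the table may have been meant for every group. This supports naming the group.

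Finally, the six high pairs may not be errors. Replacing the fixed 50% with a Beta(200,200) comparator, which the documents do not mention, reproduces all 43. That model has no follow-up term either.

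**Conclusion.** The concern holds. The boundary is sound for complete outcomes but is applied to incomplete ones, and no section supplies the missing horizon or follow-up condition. The conclusion about an uncrossed boundary needs only the rule's wording and the fact that recurrence takes time.

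The size depends on assumed accrual and timing. It runs from no shortfall at 10 per year with exponential timing to almost no chance of stopping at 33 per year, true 60%, when recurrences are spread over two years or more. If three years is intended, slow accrual instead makes the rule stop too often. Because this is the plan's only quantified recurrence safeguard and wording can repair it, it should be corrected before the boundary is relied on.

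**What to change.** Keep the 50% / 0.80 criterion and the printed pairs. Under Stopping Boundaries:

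1. Replace adverse events with recurrence within a stated horizon; 36 months from surgery would match section 16.2. Say whether locoregional or any recurrence counts.
2. Name the group (Group I, if intended).
3. Tie each pair to a fixed cohort: n counts recurrences within the horizon among the first m patients treated. Recheck every m already reached at each quarterly review, and stop if any pair is crossed.
4. State that not crossing at a given m is conclusive only when all m patients have recurred or reached the horizon.
5. State how deaths and losses before the horizon count, the expected accrual rate, and the operating characteristics at that rate.
6. Correct or explain the six high pairs.

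A fixed cohort's count can only rise, so an early crossing is never reversed, and the chance of ever crossing equals the complete-outcome figures in step 2 of the working at any accrual rate. A time-to-event posterior is a valid alternative but would replace the printed pairs.

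The cost is wording and one count per m at reviews already planned, with no new patients or data. Probability of crossing before patient 100 is treated, at true 60% / 70%, over the three assumed timings:

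| Accrual per year | Fixed-cohort rule, quarterly |
|---|---|
| 10 | 0.92-0.95 / 1.00 |
| 20 | 0.86-0.93 / 0.99-1.00 |
| 33 | 0.57-0.91 / 0.87-1.00 |
| 50 | 0.14-0.88 / 0.37-0.99 |

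Fast accrual with late recurrence is therefore not cured. A 60-month horizon acts later still (0.58 / 0.88 at 20 per year, exponential timing). Waiting until all m patients reach 36 months has the same chance of ever crossing but acts much later (0.05 before patient 100 at 33 per year, true 60%). At 20 per year with exponential timing, the chance of ever stopping rises from about 0 to 0.13 at true 40% and from about 0.01 to 0.53 at true 50%; both are the rates built into the plan's own pairs.
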